10.4. Electrocardiogram

The following ECG values will be included for summarization:

- QTcB – Bazett’s Correction
- QTcF – Fridericia’s Correction
- PR Duration
- QRS Duration
- QT Duration
- RR Duration
- Ventricular Rate

QTcF is the primary measure of corrected QT, with Bazett’s correction serving as a supportive measure. For all ECG measurements, actual values and change from baseline will be summarized continuously by visit.

The proportion of patients with ECG outliers will be presented overall and by visit. For this analysis, the categories defined below will be used:

- QT > 480 milliseconds (ms), QT > 500 ms, Female: QTcF > 470 ms, and Male: QTcF > 450 ms
- PR < 120 ms, PR > 200 ms

The interpretation of ECG results will be presented by visit (‘Normal’, ‘Abnormal, not clinically significant’, ‘Abnormal, clinically significant’).

ECG abnormalities upon first dose of study drug will be summarized categorically, with the types of abnormalities sorted alphabetically within each time point.

10.5. Pulmonary Function Testing

The following pulmonary function test outcomes will be summarized continuously:

- Largest forced expiratory volume in 1 second (i.e., FEV₁)
- Percent of predicted FEV₁
- Largest forced vital capacity (i.e., FVC)
- Percent of predicted FVC
- DLCO corrected for hemoglobin

The actual value, change, and percent change will be summarized by visit. It is noted that the percent predicted value for a given outcome is the ratio of the original value relative to the predicted value, reported as a percentage.

DLCO is collected at the local lab for each site where available, so results may be collected in domestic or SI units. DLCO results in domestic units (mL/min/mmHg) will be converted to SI units (mmol/min/kPa) prior to analysis using the following conversion factor:

- $\text{DLCO in SI units} = (\text{DLCO in domestic units}) / 2.986$

An abnormality is defined as percent predicted FEV1 < 70% and <80% of baseline or percent predicted FVC < 70% and <80% of baseline. Abnormalities will be summarized by number and percent by visit and shift tables.

A listing of pulmonary abnormalities will be provided.

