31. Planned concurrent treatment with immunosuppressive agents (e.g., azathioprine, 6-MP, or methotrexate) after enrollment. Patients receiving azathioprine, 6-MP or methotrexate at Screening must discontinue treatment with these agents prior to first dose of investigational drug.
32. Chronic non-steroidal anti-inflammatory drug (NSAID) use (Note: occasional use of NSAIDs and acetaminophen [eg, headache, arthritis, myalgias, or menstrual cramps] and aspirin up to 325 mg/day is permitted)
33. Treatment with Class Ia or Class III anti-arrhythmic drugs) or treatment with two or more agents in combination known to prolong PR interval
34. Treatment with any of the following drugs or interventions within the corresponding timeframe:
 - At Day 1
 - CYP2C8 inhibitors (eg, gemfibrozil or clopidogrel) or inducers (eg, rifampicin)
 - Two weeks prior to Day 1
 - Monoamine oxidase inhibitors (eg, selegiline, phenelzine)

Exclusions Related to Laboratory Results:

35. Serum creatinine > 1.4 mg/dL for women or > 1.6 mg/dL for men
36. Liver function impairment or persisting elevations of aspartate aminotransferase (AST) or alanine aminotransferase (ALT) > 2 times the upper limit of normal (ULN), or direct bilirubin > 1.5 times the ULN
37. Platelet count < 100,000/ μ L
38. Hgb < 8.5 g/dL
39. Neutrophils < 1500/ μ L
40. Absolute WBC count < 3500/ μ L
41. Absolute lymphocyte count < 800/ μ L
42. Electrocardiogram showing any clinically significant abnormality (e.g., acute ischemia, any significant heart conduction abnormality [e.g., left bundle branch block])
43. Forced expiratory volume at 1 second (FEV1) or forced vital capacity (FVC) < 70% of predicted values at Screening

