 - Any condition that might affect the outcome of pulmonary function testing including infection, respiratory symptoms, occupational exposures (including asbestos) and cigarette smoking needs to be collected before PFT testing and transcribed to the pulmonary function tests eCRF page. If patients have decline in PFT values (FEV1 and/or FVC) below 50% of the predicted values, treatment should be discontinued. If a patient discontinues due to respiratory AE, the Investigator should ensure that the patient has adequate evaluations as clinically indicated by a pulmonologist (consider PFTs, chest X-ray or high resolution computed tomography, based on findings of the other exams) at the time of the AE. For patients with pulmonary nodules, lung biopsy should be considered (Cryptococcus pneumonia and pulmonary TB have been reported with fingolimod). Further evaluations will be conducted until such time as resolution is confirmed or no further improvement is expected by the Investigator (based on a follow-up period of not less than 3 months).
- Hepatic effects
 - If patients have elevations in the LFTs (ALT or/and AST) \geq 3x ULN, a retest should be performed as soon as possible but not later than 14 days after the original test. If the abnormality is confirmed, weekly testing should continue until ALT and AST are $<$ 3x ULN. If the ALT and/or AST stabilizes at a level $>$ 3x ULN, the Medical Monitor may agree to less frequent testing. The Investigator should establish causality.
 - At any time, if any of the following occur and there are no apparent alternative causes for the finding, the investigational drug must be permanently discontinued:
 - ALT or AST $>$ 8x ULN or
 - ALT or AST $>$ 5x ULN with confirmation, within 2 weeks or
 - ALT or AST $>$ 3x ULN and (total bilirubin $>$ 2x ULN or INR $>$ 1.5) or

- ALT or AST > 3x ULN with the appearance of fatigue, nausea, vomiting, or right upper quadrant pain or tenderness, fever, rash and/or eosinophilia (>5%)

Investigator should establish causality.

After discontinuation due to elevation of ALT or AST > 5x ULN or concurrent elevations of ALT or AST > 3x ULN and bilirubin > 2x ULN, further liver function evaluation should be performed (for example, coagulation panel and alkaline phosphatase) in consultation with the Medical Monitor.

- Evaluation of alternative causes for the liver test abnormalities could include any of the following:
 - Acute viral hepatitis
 - Alcoholic or autoimmune hepatitis

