10.1.7. Adverse Events of Special Interest

Target treatment emergent adverse events of special interest (AESIs) will be closely monitored in the trial. AESIs include bradycardia and heart conduction abnormalities (e.g., symptomatic bradycardia, 2nd degree AV block, QT prolongation), pulmonary effects (significant decline in forced expiratory volume in 1 second [FEV₁], forced vital capacity [FVC], and diffusing capacity of the lung for carbon monoxide [DLCO] measurements), hepatic effects (confirmed liver function test (LFT) elevations > 3x ULN), macular edema based on abnormal OCT findings or visual signs/symptoms of new onset or worsening macular edema, serious or opportunistic infections and malignancies.

AESIs will be summarized by SOC and PT and presented in a listing.

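### SAP 10.5's combined lung-function rule leaves some falls of more than 20% uncounted and gives a shift table with only one possible baseline row

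*SAP*

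**What the plan says.** SAP 10.5 (Pulmonary Function Testing) defines one abnormality flag. For FEV1: "An abnormality is defined as percent predicted FEV1 < 70% and <80% of baseline". It continues for FVC: "or percent predicted FVC < 70% and <80% of baseline". The word *or* joins FEV1 to FVC; within each measure the two limits are joined by *and*.

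The flag drives three outputs. On tables: "Abnormalities will be summarized by number and percent by visit and shift tables". On listings: "A listing of pulmonary abnormalities will be provided".

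The same section also has a summary that does not use the flag: "The actual value, change, and percent change will be summarized by visit". It covers FEV1 and FVC, their percent-predicted values, and DLCO. SAP 5 includes the minimum and maximum in continuous summaries and lists all safety data by patient.

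Three other places bear on the rule:

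- Protocol 8.2, criterion 43, excludes: "Forced expiratory volume at 1 second (FEV1) or forced vital capacity (FVC) < 70% of predicted values at Screening".
- Protocol 12.2.7 sets a discontinuation level for FEV1 and/or FVC: "below 50% of the predicted values, treatment should be discontinued".
- SAP 10.1.7 names among the AESIs: "pulmonary effects (significant decline in forced expiratory volume in 1 second", with FVC and DLCO alongside. It gives no number for a significant decline. It tabulates AESIs by system organ class and preferred term and lists them.

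**The concern.** The two limits answer different questions. Percent predicted says how low lung function is; percent of baseline says how far it has fallen. Requiring both means that neither is counted alone. A patient who starts high can lose a large share of lung function and stay uncounted by ending at or above 70% predicted. A patient who starts near the entry limit can drop below it and stay uncounted because the fall is 20% or less.

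Pulmonary effects are a named AESI, worded in SAP 10.1.7 as a decline, and long-term safety is the Extension Period's primary objective. A reader of the report would expect a count of patients whose measured FEV1 or FVC declined. The plan has none.

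The planned shift table has a separate fault: part of the flag is defined relative to baseline, so it cannot classify the baseline value itself.

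**Working it through.** The plan states no figure for this rule, so there is nothing to reproduce. The check is the arithmetic of the definition.

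**Inputs.** The limits of 70% predicted and 80% of baseline come from SAP 10.5. The lowest eligible baseline, 70% predicted, comes from Protocol 8.2, criterion 43. Protocol Table 2 schedules lung-function tests before dosing only at Screening, and SAP 5.5.1 takes the last value on or before the first dose as baseline, so an eligible patient's scheduled baseline is at least 70. I hold each patient's predicted value fixed, so that the ratio to baseline is the same in litres and in percent predicted.

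**Formula.** With baseline B (% predicted), a follow-up value is counted only if it is below min(70, 0.8 × B). The limits cross at B = 70 / 0.8 = 87.5. The largest uncounted relative fall is (B − min(70, 0.8 × B)) / B.

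| Baseline B | 0.8 × B | Counted only below | Largest uncounted fall |
|---|---|---|---|
| 70 | 56 | 56 | 20.0% |
| 75 | 60 | 60 | 20.0% |
| 80 | 64 | 64 | 20.0% |
| 87.5 | 70 | 70 | 20.0% |
| 90 | 72 | 70 | 22.2% |
| 100 | 80 | 70 | 30.0% |
| 110 | 88 | 70 | 36.4% |
| 120 | 96 | 70 | 41.7% |

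**Baseline above 87.5.** Only the 70% limit binds. A fall from 100 to 71 is a 29% loss and is not counted.

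**Baseline 70 to 87.5.** Only the 80% limit binds. Every fall of more than 20% is counted; for example, 80 to 60 is 75% of baseline and is flagged. What is missed is a value between 0.8 × B and 70. The range runs from 56 to 70 at baseline 70 and from 64 to 70 at baseline 80, and it vanishes at 87.5. For example, 75 to 61 gives 61 / 75 = 81.3% of baseline: uncounted, though below the entry limit.

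**The 50% level.** For eligible baselines the flag limit is never below 0.8 × 70 = 56. Every value below 50% predicted is therefore already counted and listed.

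**Shift table.** At baseline the ratio to baseline is 100%, which is never below 80%. No patient can be abnormal at baseline, so only one baseline row can be filled.

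**How many patients.** The documents give no baseline distribution. Purely as an illustration, I assume a normal distribution truncated at 70, with mean 90 to 105 and SD 10 to 15. Then 61% to 96% of patients start above 87.5. If every patient fell by 25%, those with B of at least 70 / 0.75 = 93.3 would go uncounted: 38% to 88%. For a 30% fall the cut is 70 / 0.70 = 100, and the range is 16% to 69%. These ranges show how strongly the answer depends on baseline; they do not estimate what happened in the trial.

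**The case against.** The best defence is that the declines are not hidden. Change and percent change are summarized by visit with a minimum, so the largest fall at each visit is printed. All safety data are listed by patient, in a trial of about 60. A decline reported as an adverse event enters the AESI tables whatever the flag says. A combined rule is also a legitimate choice, because it trades sensitivity for specificity: a patient who enters at 71% and later reads 69% (69 / 71 = 97.2% of baseline) is not called abnormal. No document requires a decline-only category.

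Most of this stands, and it limits the point. It does not supply the missing count. A minimum describes one patient, not how many declined. A mean barely registers an individual: one 30-point fall among 60 patients moves it by 30 / 60 = 0.5 points. The AESI tables depend on someone reporting the decline.

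A reader might infer more than the documents support:

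- *The flag is the only categorical summary of the pulmonary AESI.* It is not: SAP 10.1.7 tabulates AESIs independently of it.
- *Large declines are labelled normal, or all are missed.* The SAP applies no such label to lung function, and falls of more than 20% are missed only from baselines above 87.5%.
- *The summary is biased towards showing no effect.* The trial has one arm and no hypothesis test, and no effect is estimated from this count. What can be said is that the count omits certain declines.
- *Patients below the 50% discontinuation level escape.* They do not, as shown above.
- *The revision log suggests the rule was loosened.* SAP Appendix 5 records only that the definition was revised. The previous definition is not shown, so the direction of change is unknown.

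**Conclusion.** The point holds as a gap in the categorical safety tables. For baselines above 87.5% predicted, the counts, shift tables and abnormality listing leave out falls of more than 20% that end at or above 70% predicted. The largest such fall is about 22% at baseline 90, 30% at 100 and 36% at 110. For baselines from 70% to 87.5%, they leave out values between 0.8 × baseline and 70% predicted; these are falls of 20% or less, but they end below the trial's entry limit. No table counts patients with a measured decline, although SAP 10.1.7 describes the pulmonary AESI in those terms. The shift table can have only one baseline row by construction.

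The thresholds follow from the SAP's definition, given an eligible baseline and a stable predicted value. The number of patients affected cannot be derived from the documents. The remedy is a modest improvement in presentation; no estimate is invalidated.

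**What to change.** In SAP 10.5, tabulate by visit and overall, separately for FEV1 and FVC, the number and percent of patients with:

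- (a) a value below 80% of baseline;
- (b) a value below 70% predicted;
- (c) both, which is the current definition.

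List every patient who meets (a) or (b). State whether the baseline ratio uses percent predicted or litres.

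Base the shift table on percent-predicted category instead of the combined flag. A single cut at 70% would still put all eligible patients in one baseline row, so the range above 70% needs at least one further division if the table is to show movement from different starting levels. The documents give no such cut, and the sponsor would have to specify it.

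A row for below 50% predicted is optional. It would make the protocol's level visible but would recover no missed cases.

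The limits in (a) to (c) are already in SAP 10.5 and the data are already collected. The cost is a few more table rows and more flagged patients to describe, some with small changes, such as the 71% to 69% case, which would enter row (b). Keeping row (c) beside the others lets the reader separate these from the combined abnormality.

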10.6. Physical Examination

Physical examination results will be listed only.

10.7. Other Assessments

A summary table of number and percent of patients with dermatological abnormalities by visit will be presented. This table will further include summary of last available value, and an overall summary. Listings of dermatological abnormalities and abnormalities found during optical coherence tomography (OCT) will be provided.

Listings of abnormalities in visual acuity and dilated ophthalmoscopy will be provided.

11. INTERIM ANALYSIS

11.1. Interim Analysis

Due to the open-label nature of this study, there is no formal interim analysis of efficacy for this trial (i.e., no p-values will be produced and no adjustment for Type I error rates is needed).

However, accumulating efficacy and safety results may be summarized and presented at various Congresses, Proceedings, Conferences, or in scholarly journals in an ongoing manner. Also, data may be periodically extracted and summarized for inclusion in regulatory filings, annual safety reports, or abbreviated safety CSRs.

11.2. Data Safety Monitoring Board

An overall summary that may include disposition, safety, and efficacy data from the trial may be presented to an independent DSMB as needed.

12. CLARIFICATIONS/CHANGES TO THE PROTOCOL PLANNED ANALYSES

The primary purpose of this section is to modify and/or clarify items specified in the Protocol [A Phase 2, Multi-Center, Open-Label Induction Trial with Extension Period to Assess Endoscopic Improvement and Changes in Intestinal and Serum Biomarkers in Patients with Moderately to Severely Active Crohn's Disease Receiving Oral RPC1063 as Induction Therapy, Version 5.0, dated May 29, 2019], as follows:

- GHAS and RHI and related endpoints are added to Section 4.2.1
- Protocol Section 6.2. Endpoints

A treatment failure criteria is defined Section 9.1. Patients identified as Treatment Failures will be listed and a sensitivity analysis of the endoscopic endpoints undertaken.

- Protocol Section 6.2.1 Induction Endpoints (i.e., Week 12)
 - [REDACTED]
 - [REDACTED]
 - [REDACTED]
 - [REDACTED]
 - [REDACTED]
 - The intestinal mucosa histopathologic features and disease activity endpoints have been revised to reflect two specific measures: the Geboes Histology Activity Score (GHAS) and the Robarts Histopathology Index (RHI)
- Protocol Section 6.2.2 Extension Endpoints (i.e., Week 52)
 - Per Section 4.2.3, all Induction Period endpoints will be replicated for the Extension Period
 - Section 4.2.3 describes additional endpoints for the Extension Period not applicable to the Induction period
 - The endpoints and analyses in Section 9.5 are not discussed in the Protocol
- [REDACTED]
- [REDACTED]
- [REDACTED]
- [REDACTED]

[REDACTED]

APPENDIX 1. IMPUTATION OF PARTIAL AND MISSING DATES

Incomplete Dates of CD Symptom and CD Diagnosis

If day is missing, day will be set to 15th of the month.

If month is missing, month and day will be set to July 1st.

If either imputation above results in a date < informed consent, then impute it as the date of informed consent -1.

Adverse Event

All AE onset dates must be entered on the eCRF as complete dates. In the rare case that all or part of an AE onset date is missing but an AE resolution date is present and after first dose date then the AE onset date will be imputed as follows:

Table 8. Adverse Event Date Imputation Rules

Year of onset	Month of onset	Day of onset	Onset date to be imputed as
Missing	Missing	Missing	Date of first dose
year = year of first dose	Missing	Non-missing	Set month to month of first dose
year = year of first dose	Missing	Missing	Set month and day to those of first dose
year < year of first dose	Missing	Non-missing	set month to December
year < year of first dose	Missing	Missing	set month and day to December 31
year > year of first dose	Missing	Non-missing	set month to January
year > year of first dose	Missing	Missing	set month and day to January 1
year = year of first dose	Month = month of first dose	Missing	Set day as day of 1 st dose
year = year of first dose	Month < month of first dose	Missing	Set day as last day of onset month
year = year of first dose	Month > month of first dose	Missing	Set day as first day of onset month
year < year of first dose	Non-missing	Missing	Set day as last day of onset month
year > year of first dose	Non-missing	Missing	Set day as first day of onset month

If AE resolution date is present and prior to first dose date, no need to impute incomplete AE start date, as the AE is not treatment emergent and the event should be in the medical history.

Prior and Concomitant Medications

- If year and month are present and day is missing then set day to first day of month for start date, and set day to last day of month for end date

- If year and day are present and month is missing then set month to January for start date, and set month to December for end date
- If year is present and month and day are missing then set month and day to January 1 for start date, and set month and day to December 31 for end date
- Completely missing dates will not be imputed

If start date is completely missing and end date is not prior to the first dose, then the medication will be classified as concomitant; if the end date is missing, then the medication will be classified as concomitant. Medications for which the start and end dates are completely missing will be classified as concomitant.

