8. SELECTION AND WITHDRAWAL OF PATIENTS

8.1. Patient Inclusion Criteria

To be eligible to participate in this trial, candidates must meet the following inclusion criteria:

1. Male or female patients aged 18 to 75 years, inclusive
2. Diagnosis of Crohn's disease for at least 2 months (prior to Screening) by clinical endoscopic evidence and corroborated by a histology report (Note: histopathology may be performed during Screening if no prior report is readily available).
3. Crohn's disease Activity Index score of 220 to 450 inclusive with an SES-CD score of ≥ 6 . (If disease isolated to ileum, the requirement will be a SES-CD score ≥ 4 .)
4. Average daily stool score ≥ 4 points and/or an average daily abdominal pain score of ≥ 2 points.
5. Patients must meet one of the following criteria:
 - Have an inadequate response or loss of response to at least one of the following Crohn's disease treatments :
 - Aminosalicylates, oral aminosalicylates ≥ 2.4 g/day or ≥ 3 g/day sulfasalazine for at least 4 weeks
 - Corticosteroids, oral prednisone ≥ 30 mg or budesonide ≥ 9 mg for at least 2 weeks or an equivalent (to oral prednisone) of intravenous corticosteroid for 1 week
 - Immunomodulators, oral azathioprine ≥ 1.5 mg/kg or 6-mercaptopurine 0.75 mg/kg (documentation of therapeutic level of 6-thioguanine is also acceptable) or methotrexate ≥ 12.5 mg/week for at least 8 weeks
 - Biologic therapy (TNF α antagonist or vedolizumab only) at an approved labeled dose used for induction therapy for at least 4 weeks or recurrence of disease activity despite scheduled maintenance therapy. (Biologic therapy exposed patients will be capped at 50% of total enrolled patients)
 - And/or have been intolerant to any of the above mentioned therapies (e.g., unable to achieve doses, dose levels, or treatment durations because of treatment related side effects and/or laboratory abnormalities)
6. The following background therapies for Crohn's disease will be permitted on a stable dose:
 - Oral aminosalicylates (e.g., mesalamine, sulfasalazine, olsalazine, balsalazide) at a stable dose for at least 3 weeks prior to Screening endoscopy
 - Prednisone (doses ≤ 20 mg per day) or equivalent at a stable dose (dose ≤ 9 mg per day) for at least 2 weeks prior to Screening endoscopy
 - Budesonide therapy at a stable dose for at least 2 weeks prior to Screening endoscopy

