13.3. Disposition, Demographics and Baseline Characteristics

The number and percentage of patients in each population will be summarized. Patient disposition, including the number of patients enrolled, dosed, completing the Induction Period, and not completing the Induction Period by reason for dropout, entering the Extension Period, completing the Extension Period, and not completing the Extension Period by reason for dropout will be summarized. Patient demographics will be summarized and will include age, sex, race, ethnicity, height, weight, and body mass index.

Baseline characteristics will be summarized for and will include age at CD symptom onset, age at CD diagnosis, years since CD symptom onset, years since CD diagnosis, baseline CDAI score, baseline SES-CD score, baseline PRO2 score, prior anti-TNF use, and prior corticosteroid use.

Compliance with investigational drug will be summarized and will include the number of patients estimated to be < 80% compliant, 80 to 100% compliant, and > 100% compliant. The total dose and average daily dose will also be summarized.

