7.2.2. Crohn's Disease History

The following CD history parameters will be summarized for the ITT population using descriptive statistics:

- Age at CD symptom onset (yr)
- Age at CD diagnosis (yr)
- Years since CD symptom onset
- Years since CD diagnosis
- Years since CD diagnosis category (0 - <2, 2 - <5, 5 - <10, 10 - <15, and ≥15)
- CDAI score at baseline
- CDAI score at baseline category (<330 and ≥330)

- Baseline Stool Frequency (daily average)
- Baseline Abdominal Pain (daily average)
- Category of days available for stool frequency and abdominal pain calculations (< 3, 3-6, >=7)
- SES-CD at baseline
- SES-CD at baseline category (< 12 and ≥ 12; ≥ median, < median)
- Baseline PRO2
- Baseline SF&AP
- Prior Corticosteroid use (Y/N)
- Prior Immunomodulator use (Y/N)
- Prior Biologics use (Y/N)
- Prior 5-ASA use (Y/N)
- Prior CD surgery History (Y/N)
- Baseline Fecal Calprotectin (microgram/g)
- Baseline Fecal Calprotectin (microgram/g) category (<250 and ≥250)
- Baseline CRP (mg/L)
- Baseline CRP (mg/L) category (<10 and ≥ 10)
- Baseline Enterocutaneous and/or Perianal Fistulas (Y/N)
- Draining Fistulas (Y/N)
- Non-Draining Fistulas (Y/N)
- Closed Fistulas (Y/N)
- Biological Response (Biologic Primary Non-responder vs All Others)
- Disease Location (Ileum only; Colon only; Ileocolonic (Ileum and Colon))
- Prior CD Surgery (Y/N)

Incomplete diagnosis dates will be imputed as detailed [Appendix 1](#).

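### The consent-date check for partial Crohn's symptom-onset and diagnosis dates has its inequality reversed: plausible past dates become the day before consent, and dates on or after consent go uncorrected

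*SAP*

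**What the plan says.** Under the title "Incomplete Dates of CD Symptom and CD Diagnosis", SAP Appendix 1 gives three instructions in sequence:

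1. "If day is missing, day will be set to 15th of the month".
2. "If month is missing, month and day will be set to July 1st".
3. "If either imputation above results in a date < informed consent, then impute it as the date of informed consent -1".

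SAP 7.2.2 (Crohn's Disease History) relies on these rules: "Incomplete diagnosis dates will be imputed as detailed" in Appendix 1. The table in that section reports age at, and years since, symptom onset and diagnosis. It also has a row for "Years since CD diagnosis category", with bands 0 to <2, 2 to <5, 5 to <10, 10 to <15 and 15 or more years. Protocol 13.3 names the four continuous variables as baseline characteristics: "age at CD symptom onset, age at CD diagnosis, years since CD symptom onset, years since CD diagnosis".

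Inclusion criterion 2 (Protocol 8.1) requires the Crohn's diagnosis to be at least 2 months old at Screening. Nothing else in the supplied text modifies the Appendix 1 rule, and the revision history (SAP Appendix 5) records no change to it.

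**The concern.** Setting a date to the day before consent makes sense only as a cap on a filled-in date that lands on or after consent. A date that already precedes consent needs no such move. As written, the third instruction acts on the dates that are fine and ignores those that are not.

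If it is programmed literally, the first two instructions have almost no effect. For a patient with a partial date, years since onset or diagnosis becomes about 0, and age at onset or diagnosis becomes about age at consent. The error runs almost entirely in one direction: disease looks newer and onset looks later. In a single-arm trial of about 60 patients, these rows tell the reader who was studied. A one-day disease duration also contradicts the trial's own 2-month criterion.

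**Working it through.** The plan gives no figure to reproduce here, so the check applies the rule to dates.

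**Inputs.** From the documents: the three instructions in SAP Appendix 1, the duration bands in SAP 7.2.2, the 2-month minimum in Protocol 8.1, and about 60 patients. Assumed: consent marks the start of Screening; symptom onset is no later than diagnosis; years since diagnosis = (consent date − diagnosis date) / 365.25. The supplied text gives no reference date for duration.

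**Rule as written.** If filled-in date < consent, use consent − 1 day; otherwise keep it.
**Rule corrected.** If filled-in date >= consent, use consent − 1 day; otherwise keep it.

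**Example 1: day missing.** Diagnosis June 2006, consent 1 March 2016.
- Filled-in date 15 June 2006: 3,547 days before consent; 3,547 / 365.25 = 9.71 years, band 5 to <10.
- As written: 29 February 2016; 1 / 365.25 = 0.003 years, band 0 to <2.
- Corrected: stays at 15 June 2006.

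**Example 2: only the year known.** Diagnosis 2016, consent 1 March 2016.
- Filled-in date 1 July 2016: 122 days after consent; −122 / 365.25 = −0.33 years.
- As written: left uncorrected. Corrected: 29 February 2016.
- This is the extreme case. Under the 2-month criterion, the only 2016 diagnosis date that allows consent on 1 March is 1 January.

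**Enumeration.** Take every consent date in 2016 (366) with every diagnosis date from 2 months to 20 years earlier, equally weighted: 2,651,669 pairs. Treat each date as partial and compare the band with that of the true date.

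| | Day missing | Month missing |
|---|---|---|
| Overwritten, as written | 2,651,669 (100%) | 2,644,106 (99.7%) |
| Left on or after consent, as written | 0 | 7,563 (0.3%) |
| Put in a wrong band, as written | 2,406,450 (90.8%) | 2,406,450 (90.8%) |
| Wrong band, corrected rule | 11,132 (0.4%) | 133,228 (5.0%) |
| Largest date error, corrected rule | 16 days | 183 days |

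The 2,406,450 pairs are exactly those with a true duration of 2 years or more, so the as-written rule misplaces all of them. Of the 7,563 uncorrected pairs, 7,441 give a negative duration, which fits no band and is not counted in the 90.8%. The other 122 fall on the consent date and give zero.

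**Effect on the table, 60 patients.** Each affected patient with a true duration of at least 2 years adds 1/60 = 1.7 percentage points to the 0 to <2 band. With a true duration of 2 to 15 years (assumed), each lowers the mean by 2/60 = 0.03 to 15/60 = 0.25 years. For 3 to 12 such patients (assumed, 5% to 20% of 60):
- Band: 3/60 = 5 to 12/60 = 20 percentage points.
- Mean: 3 × 2/60 = 0.1 to 12 × 15/60 = 3.0 years too low.

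**The case against.** The strongest reply is that this is a slip of the pen. The intent can be read from context, and a programmer may well have coded the sensible version. The documents cannot show which was done, so the distortion is conditional on literal programming. That stands, but the SAP is the specification, and as specified the result is wrong. A fault in reading the PDF cannot be wholly excluded, although the other inequality signs in Appendix 1 and elsewhere in the SAP read sensibly.

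Several limits on size also stand:

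- The 90.8% depends on the assumed range of durations. With ceilings of 5, 10 and 40 years in place of 20, the day-missing figure is 62%, 81% and 95%. The 100% among true durations of 2 years or more does not depend on that range.
- Uncorrected late dates are rare in the enumeration (0.3%, month missing only). Their sign depends on the reference date: if duration ran to a first dose 35 days after consent, 3,762 of the 7,563 would not be negative.
- The bands apply to time since diagnosis only, not symptom onset.
- SAP section 5 uses non-missing denominators for baseline percentages, so 1/60 is approximate.
- The number of patients with partial dates is not given and could be zero.

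None of this makes the written rule correct.

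**Conclusion.** The rule is wrong as written. Followed literally, it replaces nearly every partial Crohn's onset or diagnosis date with the day before consent. It puts every affected patient with at least 2 years since diagnosis into the 0 to <2 band, and it does not correct the few dates that fall on or after consent. That conclusion needs only the 2-month criterion and, for symptom dates, the assumption that onset is no later than diagnosis. The effect on the actual table cannot be fixed without the count of partial dates; the 5 to 20 points and 0.1 to 3.0 years are illustrations.

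Severity is minor. Only patients with partial dates are affected, and only in descriptive baseline rows. No efficacy or safety analysis in the supplied text uses these dates, the primary SES-CD endpoint is untouched, and the trial tests no hypothesis. SAP Table 6 and section 9.5 are not in that text, so their use of disease duration could not be checked.

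**What to change.** In the third instruction of SAP Appendix 1, change `<` to `>=` before the reference to informed consent, and keep the day before consent as the common fallback for symptom onset and diagnosis. This is one symbol, with no new data and no other change to the SAP text.

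The sponsor should also confirm whether the derivation program followed the written or the intended rule. SAP Appendix 5 shows that Week 12 and Week 52 topline tables had already been generated. If the written rule was used, the disease-history rows need to be re-run.

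One small inconsistency remains after the fix: a capped diagnosis date is one day before consent, which still conflicts with the 2-month criterion. In the enumeration this concerns at most the 7,563 month-missing pairs (0.3%). All of these are same-year diagnoses, so their duration band is unaffected.
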